## 9 STUDY DESIGN

The antiviral efficacy of the combination of interferon alpha-2b and rintatolimod will be evaluated by administering fixed doses of each drug. Subjects will receive 1 day of the combination (Day 1), followed by 1 day of observation and the same regimen on Day 3 (or Day 4), according to the safe established dosing levels (see Table 1). During this time, subjects will be monitored continuously for safety (refer to Section 19.2.1). As the standard of care therapy for COVID-19 is evolving, all patients will receive optimal standard of care that will be administered concurrently with the study drug regimen. In a double-blind, randomized, multi-center, placebo-controlled trial of intravenous remdesivir in adults hospitalized with COVID-19 with evidence of lower respiratory tract involvement, remdesivir treatment resulted in shortening the time to recovery by 4 days (43). Though 14-day survival was greater in remdesivir recipients, the difference was not statistically significant (43). Adults hospitalized with COVID-19 with evidence of lower respiratory tract involvement will be offered remdesivir through an EUA if and when this drug is available to us. If we're not able to offer remdesivir to all patients based on drug availability, we expect a similar proportion of patients in the study drug and control arms to have received remdesivir, and the effect of remdesivir on study endpoints will be evaluated in an exploratory fashion.

Roswell Park Protocol No.: I-659920

In a multi-center controlled, open-label trial comparing a range of possible treatments in patients who were hospitalized with COVID-19, patients were randomly assigned to receive oral or intravenous dexamethasone (6 mg daily) for up to 10 days or to receive usual care alone (44). Overall, 482 patients (22.9%) in the dexamethasone group and 1110 patients (25.7%) in the usual care group died within 28 days after randomization ( $p < 0.001$ ). The survival benefit of dexamethasone was observed among patients receiving either invasive mechanical ventilation or oxygen alone at randomization but not among those receiving no respiratory support. Based on these results, dexamethasone (6 mg/day) will be given as standard of care to patients admitted with COVID-19 who require supplemental oxygen.

Nasopharyngeal swab collection: Nasopharyngeal swabs will be performed by trained nursing staff under full PPE precautions. Nasopharyngeal swabs will be obtained using a single swab for both nostrils as specified in CDC guidelines: <https://www.cdc.gov/coronavirus/2019-ncov/lab/guidelines-clinical-specimens.html>. Swabs are placed in viral media and submitted immediately on room air to the Dept. of Laboratory Medicine at Roswell Park. RT-PCR for SARS-CoV-2 testing is done under the direction of [name] (Professor of Oncology, Pathology, and Molecular Pathology). Testing for SARS-CoV-2 at Roswell Park received New York State (NYS) EUA. Roswell Park uses the New York SARS-CoV-2 Real-time RT-PCR Diagnostic Panel, which received EUA from the FDA. As a NYS-authorized laboratory for COVID-19 testing, Roswell Park's diagnostic methods are as stipulated in the New York SARS-CoV-2 Real-time RT-PCR Diagnostic Panel authorized procedures. The N1 and N2 PCR reactions target different regions of the SARS CoV-2 RNA. The New York SARS-CoV-2 Real-time RT-PCR Diagnostic Panel requires the following control materials:

- Human Specimen Control (HSC): A human cell culture preparation used as an extraction control and positive control for the RNase P primer and probe set that is extracted and tested concurrently with each specimen extraction run.
- SARS-CoV-2 Positive Control (SARS-CoV-2 Pos): Run with each batch of specimens. Monitors improper assay setup, reagent failures of rRT-PCR reagents and reaction conditions.
- No Template Control (NTC): Nuclease-free water included in each run. Monitors for reagent and system contamination.
- RNase P (RP) control in clinical samples: The RP primer and probe set is included in each run to test for human RNase P, which controls for specimen quality and demonstrates that nucleic acid was generated by the extraction process.

Two PCR reactions using N1 and N2 primer sets target different regions of the SARS CoV-2 RNA. A specimen is considered positive if both N1 and N2 Ct values are  $< 40$ . Specimens with one value  $< 40$  and one  $> 40$  after repeat testing are interpreted as "Inconclusive". Specimens which are negative show no amplification for both N1 or N2 PCR reactions. Based on our experience, N1 Ct values are typically several cycles lower than the N2 values, and therefore N1 Ct values will be used in statistical analyses.

\*Validation studies included in the assay IFU (Instructions For Use) (<https://www.fda.gov/media/134922/download>) establish a Limit of Detection (LoD) of 25 genome copies/reaction. In defining the performance characteristics of the test, the IFU shows that this limit typically correlates with Ct values below 40 cycles. To assure test performance

[figure not shown]
Roswell Park Protocol No.: I-659920

consistency, positive target controls and extraction controls are required to show Ct values < 40 cycles for test run validation. Specimens with one value <40 and one >40 after repeat testing are interpreted as “Inconclusive”.

**Table 1 Dosing**

For the Main Cohort: Interferon alpha-2b dose-escalation IV over 20 minutes on Day 1 and on Day 3 or 4. The dose-escalation will use a standard 3 + 3 design, with the following doses: 0, 5, 10, and 20 MU/M  . Subsequent patients receive IFN $\alpha$ at 20 MU/M  or at MTD + rintatolimod (200 mg) on Day 1 and on Day 3 (or 4) as well as standard of care.	Initial administration to start at 20 mL/hour and increase to 40 mL/hour after 30 minutes as per the standard at Roswell. Total duration of rintatolimod infusion: 2.5 h-3h. Tubing should be flushed with 30 to 50 mL of normal saline solution upon completion. Administration will be followed by 1 hour of observation and vital signs at 30 and 60 minutes post-infusion ( $\pm$ 5 minutes).
---	---

## 10 TREATMENT

All patients will receive best available standard of care. Depending on the severity of COVID-19 and need for hospitalization, standard of care can include, but is not limited to, monoclonal antibody formulations directed against the SARS-CoV-2 Spike protein, remdesivir, dexamethasone, and tocilizumab. Treatment in the Main Cohort will consist of lead-in single agent rintatolimod (first 3 patients on the dose-escalation component) followed by the combination of rintatolimod and dose-escalation of rIFN $\alpha$ . Intravenous (IV) rintatolimod is administered as a fixed dose (200 mg per infusion) and IV rIFN $\alpha$  dose-escalation will be a standard 3 + 3 design, with the following doses per infusion: 0, 5, 10, and 20 MU/M $^2$ . The dose-escalation phase will lead to which patients will receive IFN $\alpha$  at 20 MU/M $^2$  or at MTD + rintatolimod (200 mg). The regimen will be administered on Day 1 and on Day 3 (or 4), and EOT assessments will occur on Day 7 ( $\pm$  1 day) and Day 14 ( $\pm$  3 days). This portion of the study will allow for additional safety data and the analysis of the effect of the study regimen on nasopharyngeal viral load. Using each patient's baseline nasopharyngeal viral load, we will evaluate to what extent the study regimen reduces viral load relative to supportive care only.

Treatment in the Expansion Cohort will be IV rintatolimod is administered as a fixed dose (200 mg per infusion on Day 1 and on Day 3 (or 4). Based on the PI's judgment, additional infusions of rintatolimod at 200 mg may be administered 3 to 4 days apart. Decisions about additional rintatolimod infusions will be based on evaluation of AEs attributed to rintatolimod, particularly increased FIO $_2$  needs. A maximum of 12 rintatolimod infusions may be administered per patient. The rationale for a maximum of 12 infusions was based on discussions with leadership from AIM Immunotech regarding the expected effects of rintatolimod on innate immune responses over time based on data from patients with and without cancer. Rintatolimod activates innate immune responses through a number of mechanisms including activation of RNase L and inducing interferon stimulated genes (ISGs). Administration of rintatolimod over a number of weeks may be required for sustained activation of innate immune responses to clear SARS-CoV-2.

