## 7 STUDY TIMELINES

Main Cohort: A maximum of 44 evaluable participants will be enrolled to the study over up to 36-months. Patients will be followed until Day 30 after initiation of the study regimen.

Expansion Cohort: A maximum of 20 evaluable participants will be enrolled to the study over up to 36-months. Patients will be followed until Day 30 after initiation of the study regimen.

Enrollment in the Main Cohort and Expansion Cohort will be done concurrently. If a patient is eligible for enrollment in both the Main and Expansion Cohort and is willing to be enrolled in either cohort, priority will be given to the Main Cohort.

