### 10.1 Dosing and Administration

#### Interferon-Enhancing Regimen

For dosing, refer to **Table 1**. The regimen will be administered on Days 1 and 3 (or 4) in the following order:

- Pretreatment: 500 mL Normal saline IV over 60 minutes
- Pre-medications: acetaminophen (Tylenol®) 650 mg by mouth x 1 dose; prochlorperazine (Compazine®) 10 mg by mouth x 1 dose – administered 30 minutes ( $\pm$ 5 minutes) after starting pre-treatment hydration
- Interferon alpha-2b: (dose-escalation; maximum 20 MU/M $^2$ ) IV over 20 minutes

Rintatolimod: 200 mg IV, initial administration to start at 20 mL/ hour and increase to 40 mL/ hour after 30 minutes as per the standard at Roswell. Total duration of rintatolimod infusion: 2.5 h-3h. Tubing should be flushed with 30 to 50 mL of normal saline solution upon completion. Administration will be followed by 1 hour of observation and vital signs at 30 and 60 minutes post-infusion ( $\pm$  5 minutes).

Roswell Park Protocol No.: I-659920

Pretreatment and pre-meds listed above are recommendations and may be modified based upon institutional SOC requirements and at the discretion of the investigator. Treatment can be administered in the outpatient or inpatient setting, per the investigator's/physician's discretion.

Each daily treatment will be initiated after interval history and physical examination is performed and once the relevant laboratory studies have been confirmed to be within clinically acceptable ranges, specifically: ANC  $\geq$  1000/mm^3, total bilirubin  $\leq$  3x ULN, AST and ALT  $\leq$  5 x ULN.

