**Table 2 Treatment Related Toxicity Management**

Treatment-related AEs	Toxicity grade or conditions (CTCAE5.0)	Action taken for Interferon Alpha-2b	Action taken for Rintatolimod	Additional actions
Chills/Fever	Grade 3 that persists for $\geq$ 48 hours despite acetaminophen	None	None	Consider additional acetaminophen dosing, supportive care
Pancreatitis	Grade 3	Hold  Decreased future doses by 75% (to 5MU/M2)	Hold	Supportive measures as clinically indicated
AST / ALT elevation or Increased bilirubin	Grade 3	Hold until improved to grade 1; Decrease future doses by 75%	Hold	Advise evaluation for other possible etiologies; consider imaging
Vomiting	Grade 3 vomiting $\geq$ 48 hours despite optimal anti-emetic therapy	Hold until resolved to grade 1; Decrease future doses by 75%	Hold	
Depression or other clinically relevant mood disorder	Grade 3	Permanently discontinue; appropriate supportive care/intervention	None	Patients and family members will be informed in advance about the potential for depression and anxiety, including worsening of pre-existing mood disorders.
Neutropenia	Grade 3 or 4	If Grade 3, decrease future doses by 75%. If Grade 4, permanently discontinue	Hold	Transient neutropenia is expected as a result of neutrophil activation and redistribution rather than bone marrow suppression. Recent cytotoxic chemotherapy is an additional cause of neutropenia. COVID-19 is known to cause lymphopenia, but not neutropenia. For prolonged neutropenia that is not expected from the study regimen and recent chemotherapy (if applicable), the primary oncologist and a hematologist will be consulted.
Hemorrhage	Grade 2 or greater	None	None	
Myocardial infarction, stroke,		Permanently discontinue; appropriate	Permanently discontinue; appropriate	

Treatment-related AEs	Toxicity grade or conditions (CTCAE5.0)	Action taken for Interferon Alpha-2b	Action taken for Rintatolimod	Additional actions
or other arterial thrombotic event		supportive care/intervention	supportive care/intervention	
All other clinically significant AEs 	Intolerable Grade 2 or Grade 3	Hold therapy until resolved to Grade 1 or baseline; reduce future doses by 75%	Hold therapy until resolved to Grade 1 or baseline; reduce future doses by 50%	
	Grade 4	Permanently Discontinue	Permanently Discontinue	

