### **11.1 Screening**

Within 3 days prior to treatment initiation and may be the same day as initiation of study treatment:

- Recording of concomitant medications
- Medical and Surgical History
- Physical exam (lung auscultation), Vital Signs and weight;  $\text{SaO}_2$
- ECOG Performance Status Assessment
- Hematology
- Chemistry
- Arterial blood gas

Roswell Park Protocol No.: I-659920

- Serum HCG pregnancy testing (within 3 days of Day 1 in women of child-bearing potential only)
- EKG
- Chest X-ray or CT imaging (NOTE: If a chest CT is ordered as standard of care prior to starting treatment, a chest x-ray is not required)
- Nasopharyngeal swab
- Evaluations Performed on each day of treatment [(Day 1 and Day 3 (+ 1 day)]: Recording of concomitant medications
- Recording of Adverse Events
- Targeted physical exam
  - Auscultation of lungs
  - Vital Signs (temperature, blood pressure, pulse rate and respiratory rate, SaO2) will be performed pre- treatment and at 30 and 60 minutes post rintatolimod ( $\pm$  5 minutes)
- ECOG Performance Status Assessment
- Hematology
- Chemistry
- Blood (30cc) for correlative studies: On Day 1 treatment and Day 3 treatment, prior to treatment and within 1 hour after end of infusion treatment (two draws on each of these days).
- Nasopharyngeal swabs for viral quantification by quantitative PCR

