### 17.6.2 Reporting Adverse Events

Routine AEs occurring between the start date of intervention until 30 days after the last intervention, or until the event has resolved, the study participant is lost to follow-up, the start of a new treatment, or until the study investigator assesses the event(s) as stable or irreversible, will be reported. New information will be reported after it is received.

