**Study Calendar (Expansion Basket: Rintatolimod)**

Evaluation	Screening and Informed Consent	Day 1	Day 3 (or Day 4) 	Day 7 ( $\pm$ 1 day) and Day 14 ( $\pm$ 3 days) and Day 30 ( $\pm$ 3 days) 
Written Informed Consent prior to any Screening Procedures	X			
Recording of Concomitant Medications		X	X	X
Recording of Adverse Events		X	X	X
Survival Follow-up (through Day 14)		X	X	X
Clinical Assessments				
Medical & Surgical History		X		
Physical Exam including vital signs 	X	X	X	X
ECOG Performance Status	X	X	X	X
Laboratory Procedures				
CBC with diff	X	X	X	X
CMP	X	X	X	X
Serum hCG in women of child-bearing potential	X			

Evaluation	Screening and Informed Consent	Day 1	Day 3 (or Day 4)	Day 7 (<math>\pm</math> 1 day) and Day 14 (<math>\pm</math> 3 days) and Day 30 (<math>\pm</math> 3 days)
ABG	X			
Blood (30cc) for immunologic studies 	X	X (prior to treatment) and X (within 1hr after end of infusion treatment)	X	X 2a
Nasopharyngeal Swab (as required and based on availability)	X	X	X	X
Imaging/ Other Procedures				
12-Lead ECG	X			
CXR or CT scan 	X			
Clinical evaluation of endpoints 	X	X	X	X
Study Drug Administration				
Rintatolimod Administration + best available SOC		X	X	X 

1. Hospitalization in patients who were not inpatients at study entry; respiratory failure requiring mechanical ventilation; 15-day survival.
2. Blood (30cc) for correlative studies: On Day 1 prior to treatment and within 1 hour after end of infusion treatment (two draws on Day 1). Note: The treatment begins with IV rintatolimod, with the correlative blood draw within 1 hour following IV rintatolimod as indicated above. Refer to Section 11.4.

2a: Follow-up visits- NOTE: In the event patient cannot tolerate treatment, then blood (30cc) for correlatives will be collected at time that the patient recovers from toxicities (ideally within 1 week of the infusion).

3. Physical exam will be limited to vitals and auscultation of lungs. Vital signs (temperature, heart rate, respiratory rate, blood pressure,  $\text{SaO}_2$ ), body weight, and height: Height collected at baseline only.
4. NOTE: If a chest CT is ordered as standard of care prior to starting treatment, a chest x-ray is not required.

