5. Based on the PI's judgment, additional infusions of rintatolimod at 200 mg may be administered 3 to 4 days apart, after the Day 3 (or Day 4) administration. Decisions about additional rintatolimod infusions will be based on evaluation of AEs attributed to rintatolimod, particularly increased  $\text{FIO}_2$  needs. Patients who do not receive additional rintatolimod infusions will follow the above schedule for EOT/Follow-up visit.
6. Based on the PI's judgment, additional infusions of rintatolimod at 200 mg may be administered 3 to 4 days apart. Decisions about additional rintatolimod infusions will be based on evaluation of AEs attributed to rintatolimod, particularly increased  $\text{FIO}_2$  needs. A maximum of 12 rintatolimod infusions may be administered per patient.
7. While every effort will be made to complete assessments, there are limitations for outpatients, including securing transport to Roswell Park. Some follow up visits will need to be done virtually, and in other cases, may be limited to viral swabs. These missed assessments or sample collections for outpatients will not be considered protocol violations.

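### Expansion Cohort follow-up and dated laboratory tests stop at about Day 30, but a permitted 12-infusion course runs to Day 33-44

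*Combined protocol and SAP*

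**What the plan says.** Section 10 gives Expansion patients rintatolimod on Day 1 and Day 3 (or 4). Further infusions, 3 to 4 days apart, are at the PI's judgment: "A maximum of 12 rintatolimod infusions may be administered per patient". The same section explains that treatment over several weeks may be needed.

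Section 7 says of this cohort: "Patients will be followed until Day 30 after initiation of the study regimen". In Appendix F, the Expansion calendar ends with a combined column for Day 7 (±1), Day 14 (±3) and Day 30 (±3), which includes CBC and CMP. The row "Rintatolimod Administration + best available SOC" has a mark in that column with footnote 6, the footnote that allows extra infusions. Footnote 5 points the other way: "Patients who do not receive additional rintatolimod infusions will follow the above schedule for EOT/Follow-up visit". No separate schedule is given for patients who do receive them.

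The reporting sections use a different clock. Section 17.6.2 covers "Routine AEs occurring between the start date of intervention until 30 days after the last intervention", and Section 17.7.1 sets the same period for SAEs unless a new treatment starts first.

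On laboratory tests around dosing, Section 11.1 lists hematology and chemistry for treatment days but defines those days as Day 1 and Day 3 (+1). Section 10.1 states "Each daily treatment will be initiated after interval history and physical examination is performed and once the relevant laboratory studies have been confirmed", but under the Interferon-Enhancing Regimen; the Expansion subsection does not repeat it. Section 12.1 requires end-of-treatment tests without dating them.

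**The concern.** A patient treated exactly as Section 10 permits can receive study drug after the date on which Section 7 ends follow-up. The visit schedule appears not to have been extended when longer courses were allowed; Section 10.4 still plans two doses over four days.

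Safety of rintatolimod with or without interferon is a primary objective (Section 1.1). Table 2 holds rintatolimod for Grade 3 events under "AST / ALT elevation or Increased bilirubin". In a patient without symptoms, that rule works only if a recent result exists. Section 13.2 is mixed on the need: it reports no dose-limiting organ toxicity in long-term use, but also liver enzyme rises in several patients dosed over many weeks. At stake is whether late, mainly silent laboratory toxicity is detected in the patients with the longest exposure.

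**Working it through.** The plan gives no duration for a 12-infusion course. Its only stated duration, two doses over four days (Section 10.4), is reproduced by the two-dose schedule: Day 1 to Day 4 is 4 days.

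**Inputs.** Infusion 2 on day d = 3 or 4; gap s = 3 or 4 days; maximum 12 infusions (Section 10). Follow-up ends at Day 30 (Section 7). The last dated visit is Day 30 ± 3, so Day 27 to Day 33 (Appendix F). Reporting runs to the last dose + 30 days (Sections 17.6.2 and 17.7.1).

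**Formula.** Infusion k falls on Day d + (k − 2) × s. For k = 12 this is d + 10s.

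| Infusion 2 | Gap | Infusion 12 | Infusions after Day 30 | After Day 33 | Strictly between Day 14 and Day 30 | Reporting ends |
|---|---|---|---|---|---|---|
| Day 3 | 3 | 3 + 30 = Day 33 | 1 | 0 | 5 | Day 63 |
| Day 4 | 3 | 4 + 30 = Day 34 | 2 | 1 | 5 | Day 64 |
| Day 3 | 4 | 3 + 40 = Day 43 | 4 | 3 | 4 | Day 73 |
| Day 4 | 4 | 4 + 40 = Day 44 | 4 | 3 | 4 | Day 74 |

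Letting each gap be 3 or 4 days (2 × 2^10 = 2,048 schedules) keeps the last infusion at Day 33-44, with 1-4 infusions after Day 30, 0-3 after Day 33, and 3-5 between Day 14 and Day 30. Moving those two visits within their windows widens the last range to 2-7.

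**When Day 30 is passed.** The eighth infusion falls no later than 4 + 6 × 4 = Day 28, so courses of eight or fewer finish in time. At constant 4-day gaps the ninth falls on Day 31 or 32. At constant 3-day gaps dosing passes Day 30 only at infusion 11 or 12. If Section 7 counts Day 1 as day zero, follow-up ends on Day 31, still before infusion 12.

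**Last dated laboratory test to infusion 12.** Nominally 33 − 30 = 3 to 44 − 30 = 14 days. With the visit window, 33 − 33 = 0 to 44 − 27 = 17 days.

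**Overlap with dated tests.** Infusion 3 always falls on Day 6-8 and infusion 5 on Day 12-16, both inside visit windows. A full course always has an infusion in Day 27-33. With one visit per window, up to 3 of the 10 extra infusions can coincide with a dated CBC/CMP, leaving at least 10 − 3 = 7 that do not.

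**Reporting window.** With two doses it ends on Day 33 or 34 (3 + 30 or 4 + 30), a small overrun of Day 30. A full course moves it to Day 63-74, which is 30 to 40 days later. No contact is dated in the 30 days after the infusion-12 visit.

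**The case against.** A reader might infer that safety follow-up stops at Day 30. The documents do not support that. Sections 17.6.2 and 17.7.1 run from the last dose, and Section 17.7.1 also asks for related SAEs that occur later still. Each infusion after Day 30 is an attended visit with an hour of observation and vital signs, and AEs are evaluated in deciding on each extra dose. Section 12.1 follows patients who stop for an AE, Section 17.8 follows related SAEs to resolution, and the DSMC reviews safety (weekly in Section 19.7, less often in Section 20). On this view the fault is one outdated line in Section 7. This stands as a limit on the point, but reporting rules do not create a visit or a blood test.

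A reader might also infer that extra infusions are given with no laboratory cover. That is too strong, given the overlap with dated tests. The treatment-day wording in Sections 10.1 and 11.1 could also be read as general, although the heading of one and the bracketed days of the other count against it. In the other direction, footnote 7 allows outpatient follow-up to be virtual or limited to swabs, so even the dated tests are not assured.

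A pre-dose test before every extra infusion is not something the documents require. Expansion eligibility was deliberately loosened because interferon is absent, and it sets no laboratory thresholds. This objection stands: testing before each dose is one reasonable option.

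Finally, Section 17.4 records laboratory abnormalities as AEs only if they are clinically significant and need active management, so some silent changes after the last dose would not count even if found. Section 19.1 attaches the primary safety endpoints to Phase I and Phase IIa, although Sections 1.1, 8.1 and 16.1 are worded generally. Both weaken the link to the primary safety result.

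**Conclusion.** The point holds in limited form. Section 7 ends Expansion follow-up before permitted dosing can end, and it conflicts with the reporting window in Sections 17.6.2 and 17.7.1. The gap is confined to dated follow-up and laboratory tests late in and after an extended course, and to infusions between the dated tests, where the Table 2 AST/ALT and bilirubin rule may lack a current result.

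For a full course, 1-4 infusions follow Day 30 and the last dated CBC/CMP nominally precedes the final dose by 3-14 days. These figures assume gaps of 3 or 4 days and no held doses; holds would push the last dose later. Passing Day 30 needs at least nine infusions. How many of the at most 20 patients will have extended courses is not stated.

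A reader might go further and infer that the safety results are biased. The documents show only that late laboratory toxicity could be under-ascertained. The Day 0-14 viral-load measurements are not affected.

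**What to change.** 1. In Section 7 and the Expansion calendar, define follow-up as the later of Day 30 and 30 days after the last infusion, with a safety and vital-status contact at that time (phone allowed).
2. Date the Section 12.1 end-of-treatment CBC/CMP relative to the last infusion.
3. Reconcile footnotes 5 and 6 so that the Day 7/14/30 column applies to patients given extra infusions.
4. Require a current CBC/CMP during extended dosing, drawn at existing infusion visits: either before each extra infusion or at a stated minimum frequency such as weekly.

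No dose change is needed. The cost is a calendar amendment, at most ten pre-dose draws per patient (fewer if weekly), a dated end-of-treatment test and one later contact, only for those of the at most 20 patients who receive extra infusions.
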